This will be a randomized, double-blind, placebo-controlled trial of two concentrations of intralesional triamcinolone, triamcinolone 40mg/ml and triamcinolone 10mg/ml, with normal saline as a placebo control. Target enrollment is up to 60 lesions with 1-3 lesions treated in each patient enrolled. Screening will be performed during regularly scheduled clinic visits with the principal investigator ([name]). Informed consent will be signed by the subject. Physical exam will be performed to assure that inflammatory lesions suitable for treatment are present. Once subjects are deemed appropriate for the study, between one and three treatment sites will be marked with sequential lettering with a skin marker and documented by body location. Pain level of each lesion will be recorded. At that time the triamcinolone and/or placebo will be prepared by the co-investigator the drug will be concealed with opaque tape on the syringe. The principal investigator and subject will thus be blinded as the principal investigator administers the treatment.

Following treatment, subjects will be given a paper questionnaire that will ask them to rate their level of pain on a 1-10 scale, the effectiveness of the treatment, and whether they believe the target lesions has resolved. They will record these scores on days 1, 2, 3, 5, 7, 10, and 14. These will be patient-reported outcomes only without any physician assessment as this is felt to be a more clinically relevant outcome. The principal investigator or co-investigator will contact subjects by phone to ensure that logs recording pain and days to resolution are completed in a timely and correct manner, but no data will be collected during the 14-day period in which questionnaires are completed to avoid influencing subject responses at the time of contact. After the final questionnaire is completed (more than 14 days after the intervention is performed), the

co-investigator or principal investigator will contact the subject by phone to remind the subject to mail in their questionnaires and may allow the option to collect the data that the subject has already recorded. At this time, the principal or co-investigator may also ascertain if any previously unreported adverse events occurred during the study period. The days to resolution reported and pain data will be used to compare the effects of varying concentrations of intralesional triamcinolone with normal saline.

Protocol summary:

Day 0: Subject recruited and pre-screened,

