- Adult subjects will sign adult consent form and HIPAA authorization
- Subjects aged 16-17 will sign the age 15-17 assent form and parents will sign the parental consent form. HIPAA authorization will be signed.
- History of disease and medications will be taken
- Physical exam will be performed to see if appropriate target lesions are present
- Each lesion will be randomized to a treatment group
- Treatment will be administered via intralesional injection by the principal investigator
- Follow-up paper and pencil questionnaire will be dispensed along with a stamped and addressed return envelope.

Day 1, 2, 3, 5, 7, and 10:

- subject will complete corresponding section of the paper and pencil questionnaire on each of these days to report pain level of each lesion treated and whether each lesion has resolved.
- between day 2-7 the subject will be contacted by phone and reminded to complete their questionnaires. No data will be gathered at this time.

Day 14: subject will complete corresponding section of the paper and pencil questionnaire on each of these days to report pain level of each lesion treated and whether each lesion has resolved. He/she will also answer a question regarding how they view the efficacy of the treatment for each location

Day 14-21:

- investigator or co-investigator will contact the subject by phone to remind the subject to mail the completed questionnaire or allow the option collect the data on pain, lesion resolution, and efficacy that was previously recorded during the study period over the phone. At that time, the primary or co-investigator may ascertain if any adverse effects have occurred that have not already been reported.

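### Cheap improvement, low severity: the co-investigator, who prepares the syringes and is not described as blinded, may make the follow-up calls; give them to someone unaware of allocation

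*Protocol*

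**What the plan says.** **Preparation and blinding (Protocol, Study Design).** The "triamcinolone and/or placebo will be prepared by the co-investigator the drug will be concealed with opaque tape on the syringe". The text then draws its conclusion: "The principal investigator and subject will thus be blinded as the principal investigator administers the treatment". The co-investigator is not listed as blinded.

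**Call during follow-up.** Study Design names the caller: "The principal investigator or co-investigator will contact subjects by phone to ensure that logs recording pain and days to resolution are completed" on time and correctly. It adds a safeguard: "no data will be collected during the 14-day period in which questionnaires are completed to avoid influencing subject responses at the time of contact". The Protocol summary gives the timing but no caller: "between day 2-7 the subject will be contacted by phone and reminded to complete their questionnaires. No data will be gathered at this time".

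**Call after day 14.** Study Design says the "co-investigator or principal investigator will contact the subject by phone to remind the subject to mail in their questionnaires and may allow the option" of taking answers the subject has already written down. The Day 14-21 entry of the Protocol summary words the same call differently: "remind the subject to mail the completed questionnaire or allow the option collect the data on pain, lesion resolution, and efficacy". It too limits phone collection to earlier records.

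**Adverse events.** Study Design continues: "At this time, the principal or co-investigator may also ascertain if any previously unreported adverse events occurred during the study period". The Day 14-21 entry repeats this.

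Neither document requires the caller to be unaware of allocation, or asks for phoned answers to be marked as such.

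**The concern.** Opaque tape hides the contents from the person who injects and the person who is injected. It does not hide them from the person who filled the syringe. If the co-investigator knows the allocation, the text lets someone with that knowledge speak to subjects while they are still scoring, write down their answers afterwards, and question them about harms.

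Three routes are open in principle:

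- **Cueing on the first call.** A call on days 2-7 can come before the day 5 pain score (Aim 2). It always comes before the day 10 and day 14 resolution entries (Aim 1) and the day 14 efficacy rating (Aim 3).
- **Transcription on the second call.** This matters most where the paper form never arrives and the phoned answers become the only record.
- **Adverse-event questioning.** The documents do not have subjects write down adverse events in advance, so what is recorded may depend on how the question is put.

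All three aims rest on patient-reported answers, and the SAP itself notes that reported clearance may depend on patient perception. The protocol shows awareness of caller influence by restricting what is collected in the first 14 days, but it does not restrict who calls.

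**Working it through.** The plan states no figure on this point, so the check is mainly a comparison of text.

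**Step 1. Who knows the allocation?** Study Design has the co-investigator prepare the syringe and derives the blinding of the other two parties from the tape. Nothing describes pre-coded syringes or a separate preparer. That the co-investigator knows the allocation is a reasonable inference but is not stated. Nor do the documents say that preparer and caller will always be the same person; they only permit it.

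**Step 2. What may that role do, and what already protects each contact?**

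| Contact | Caller named | Existing protection | Left open |
|---|---|---|---|
| Reminder, days 2-7 | Either investigator (Study Design); none (Protocol summary) | Blinded subject; no data taken | Caller may know allocation |
| Outcome answers by phone, after day 14 | Either investigator | Blinded subject; answers already on paper | Caller may know allocation; form may not be obtained |
| Adverse-event question, same call | Either investigator | Blinded subject | No prior written record; caller may know allocation |

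**Step 3. Is the paper form still obtained after phone collection?** Study Design joins the mailing reminder and the phone option with *and*; the Protocol summary joins them with *or*. Under the first, the form is still requested. The second can be read as making the phone a substitute. The Day 0 entry gives each subject the form and a stamped envelope, so a check against paper is possible but not secured.

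**Step 4. Does the adverse-event part reach an analysis?** No. The three Study Aims are days to resolution, day 5 pain and the patient's rating of benefit. The SAP, including Final analysis of data, compares no adverse events.

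**Step 5. How many calls would the fix restrict?**

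- Scheduled contacts per subject (Protocol summary): one on days 2-7 plus one on days 14-21 = 2, not counting repeat attempts.
- Enrolment (Protocol, Participants): 20 to 60 patients, so 2 × 20 = 40 to 2 × 60 = 120 calls.
- SAP, Simulation settings: 12 + 6 + 12 = 30 patients, so 2 × 30 = 60 calls.

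These counts measure the workload affected by the fix. They do not measure exposure or bias: the share of calls made by the co-investigator and the share of questionnaires taken by phone are not stated, and each could be anywhere from none to all. The fix changes no sample size, alpha or power.

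**The case against.** The strongest reply is that the protocol has already dealt with the outcome route. The subject is blinded and writes the scores unaided, with no physician assessment. Nothing is collected while scoring is under way. Later phone collection is a reading-out of existing entries. The day 5 pain score is due at least 14 − 5 = 9 days before the second call. Transcription error can also be made by a caller who does not know the allocation, and nothing in the documents suggests deliberate alteration. This stands, and it is why the severity is low.

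Cueing is also limited by the design. Lesions, not patients, are randomised. Under the SAP's mix with equal-chance assignment, the expected number of lesions in patients who receive more than one arm is 6 × 2 × (2/3) + 12 × 3 × (8/9) = 8 + 32 = 40 of 60. A general remark to such a patient does not favour one arm over another within that patient; only lesion-specific cueing would. This stands too, although the other 20 lesions remain exposed in principle.

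The *or* in the Protocol summary may simply list what the caller may do, without waiving the form. That is a fair reading, so the wording is treated here as a secondary record-keeping matter.

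Finally, the fix is not free. Only two callers are named, team size is not given, and missed calls could cost diaries. This stands as a disclosed downside. It is eased, though not removed, by the fact that the principal investigator is already one of the two callers.

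The reply does not meet one point: the safeguards govern what is collected and when, not who asks, and the two data safeguards do not reach the adverse-event question.

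**Conclusion.** The point holds as a cheap improvement of low severity. A role that probably knows the allocation is permitted to make both calls, take outcome answers and ask about adverse events, although a caller described as blinded is already authorised. The residual risk to the three aims is small. The adverse-event question is less protected but affects the safety record only.

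A reader might infer more, and the documents do not support it:

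- **That the trial is not double blind, or that the blind is broken.** The subject and the person giving the injection are both described as blinded.
- **That the results will be biased, or that the false-positive rate is inflated by some amount.** Any such figure would need an assumed shift in reported days or scores, for which the documents give no basis. None is offered here.
- **That the co-investigator is stated to be unblinded.** This is inferred from the preparation step.

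The conclusion assumes that whoever fills the syringe knows its contents, and that the same person may also make the calls, as the text allows.

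**What to change.** In Study Design and in the Protocol summary, including the days 2-7 entry that names no caller, state that the reminder call, the phone collection of outcomes and the adverse-event question are handled by a person unaware of allocation. That can be the principal investigator or an existing team member who did not prepare the syringes and cannot see the allocation.

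As a secondary step, align *and* with *or* so that the paper form is still requested after answers have been phoned in, and record which questionnaires came by phone.

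**Cost.** A few words of protocol text and a field for mail or phone; no added staff, visits or subjects. The 40 to 120 scheduled calls (60 at the SAP's 30 patients) would fall on fewer callers, and on the principal investigator alone if nobody else qualifies. That means more of that person's time, less backup and possibly fewer diaries returned. Allowing any existing team member who is unaware of allocation to call reduces this, but whether one is available cannot be told from the documents.

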**A randomized, controlled, double blind study to evaluate the efficacy  
of intralesional triamcinolone in the treatment of hidradenitis  
suppurativa**

STATISTICAL ANALYSIS PLAN

**NCT number** NCT02781818  
**Document Date** 05/17/2017

Date 5-17-2017

Statistical approach for IRB 16-0773, A randomized, controlled, double-blind study to evaluate the efficacy of intralesional triamcinolone in the treatment of hidradenitis suppurativa.

The calculations for power justification are outlined below demonstrating 80% power to demonstrate our primary aim. The power to tell a difference between our 2 treatment groups is only 28%, but this is acceptable as a secondary aim. In our final analysis we will use a mixed effects regression model to account for the variation in number of lesions evaluated in each patient. This will account for some correlation among lesions treated within the same patient due to how patient reported lesion clearance may be somewhat effected by individual patient perception. 95% confidence intervals will be created for each group and p-values for comparisons between each group will be calculated in the final analysis for each study end point.

Our secondary aim of finding differences in pain scores are appropriately powered with power nearing 100%.

For our third aim demonstrating improved perception of treatment, the analysis is more straightforward as data is gathered at only one time point. We will perform descriptive analysis and report the average ratings and the corresponding confidence intervals.

#### **Simulation settings for power analysis**

There are 30 patients in which 12 have 1 lesion, 6 have 2 lesions and 12 have 3 lesions. Each lesion is then randomized to one of 3 treatment groups (say, A, B, C) with equal chance. For patient  $k$ , lesion  $j$ , let  $T$  be the treatment assigned. We generate data as following:

$$Y_{kj} = \beta_1 I(T_{kj} = A) + \beta_2 I(T_{kj} = B) + \beta_3 I(T_{kj} = C) + b_k + e_{kj}$$

$b_k$  is a patient-specific random effect,  $e_{kj}$  is a random error.

We consider two scenarios, where the first one corresponds to the outcome of days to resolution, and the second one is for the pain scores.

Scenario 1:

$$\beta_1 = 6, \beta_2 = 8, \beta_3 = 10;$$

$b_k$  is patient-specific random effect from normal with mean 0 and standard deviation  $5\sqrt{0.2}$ ;

$e_{kj}$  is random error from normal with mean 0 and standard deviation  $5\sqrt{0.8}$ .

Scenario 2:

$$\beta_1 = 2, \beta_2 = 4, \beta_3 = 6;$$

$b_k$  is patient-specific random effect from normal with mean 0 and standard deviation  $\sqrt{0.2}$ ;

$e_{kj}$  is random error from normal with mean 0 and standard deviation  $\sqrt{0.8}$ .

After simulating the data 100 times, we fit the same model, and perform two tests as follows:

- Test  $\frac{\beta_1 + \beta_2}{2} < \beta_3$ , report the probability of rejecting the null (one side p-value < 0.05), report the standard error of the estimates for  $\frac{\beta_1 + \beta_2}{2} - \beta_3$ .
- Test  $\beta_1 < \beta_2$ , report the probability of rejecting the null (one side p-value < 0.05), report the standard error of the estimates for  $\beta_1 - \beta_2$ .

The results are given in the following table. It shows that for the primary outcome (days to resolution), there is 80% power to test that the combined treatment groups have less number of the days than the control group. The power to detect the difference between two treatment groups is 28%. For the secondary outcome of the pain scores, these numbers become 100%.

The average 95% confidence interval for the difference between the combined treatment groups and the control group is (2.6, 5.6) for days to resolution and (2.46, 3.52) for pain scores.

Results of the two scenarios						
Scenario	Compare combined treatments vs control			Compare two treatment groups		
	$\frac{\beta_1 + \beta_2}{2} - \beta_3$	SE	power	$\beta_1 - \beta_2$	Std err (estimates)	power
	True value			True value		

1: days to resolution	-3	1.331	0.8	-2	1.540	0.28
2: pain scores	-3	0.266	1	-2	0.300	1

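### No within-patient balance is described for lesion allocation; adding it would raise primary power by about 5 to 6.5 points with the same 30 patients and 60 lesions

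*SAP*

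**What the plan says.** The allocation rule appears in two places. In the SAP, under Simulation settings for power analysis: "Each lesion is then randomized to one of 3 treatment groups (say, A, B, C) with equal chance". In the protocol summary, under Day 0: "Each lesion will be randomized to a treatment group". Neither document mentions blocking, stratification, a fixed arm size or any restriction within a patient.

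The structure would allow such a restriction. Under Study Design, "Target enrollment is up to 60 lesions with 1-3 lesions treated in each patient enrolled", and before any syringe is prepared "between one and three treatment sites will be marked with sequential lettering with a skin marker and documented by body location". The co-investigator prepares the syringes and covers them with opaque tape; the principal investigator injects and, like the patient, is blinded. All outcomes are reported by the patient, without physician assessment.

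The SAP's opening text plans a mixed effects model because lesions in one patient share that patient's perception of clearance. The power simulation assumes "There are 30 patients in which 12 have 1 lesion, 6 have 2 lesions and 12 have 3 lesions".

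**The concern.** There are three regimens and up to three lesions per patient, and the SAP itself identifies a patient effect common to those lesions. Comparing regimens inside a patient removes that effect. If each lesion is allocated without regard to the patient's other lesions, some patients receive the same regimen more than once, and some receive no placebo or only placebo. Those patients contribute nothing to the within-patient part of the primary contrast. Total arm sizes also vary by chance.

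What is at stake is precision. The comparison remains unbiased, but the primary contrast is estimated less precisely than 60 lesions permit, in a small trial whose stated power is already higher than its own inputs give.

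**Working it through.** **Inputs (SAP, Simulation settings for power analysis).** 12, 6 and 12 patients with 1, 2 and 3 lesions (60 lesions). Mean days 6, 8 and 10 for A, B and C, so the primary contrast (A+B)/2 − C is −3. Patient variance 25 × 0.2 = 5 and error variance 25 × 0.8 = 20, so the total SD is 5 and the ICC 0.2. Test at "one side p-value < 0.05".

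**Step 1: the plan's own figure.** The SAP reports SE 1.331 and power 0.80. The SE reproduces: known-variance generalised least squares (GLS), averaged over random allocations, gives 1.357 with independent allocation and 1.334 with a forced 20/20/20 split. The power does not: Φ(3/1.331 − 1.645) = Φ(0.609) = 0.73. Simulating the SAP's model with a REML fit gives 0.70 to 0.72, depending on the critical value. The SAP used 100 simulated data sets, so its Monte Carlo SE is √(0.8 × 0.2/100) = 0.04. With a true power of 0.72, 80 or more rejections in 100 has a chance of about 4%. The starting point below is therefore about 72%.

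**Step 2: what independent allocation gives each patient.**
- Three lesions, no placebo-versus-active pair: no placebo (2/3)³ = 8/27, plus all placebo 1/27, total 9/27 = 33%.
- Two lesions, no such pair: no placebo 4/9, plus both placebo 1/9, total 5/9 = 56%.
- Three lesions, at least one regimen missing: 1 − 6/27 = 78%.

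**Step 3: SE with within-patient balance.** Three-lesion patients get A, B and C. Two-lesion patients get two different regimens, each pair used twice. One-lesion patients split 4/4/4. A patient with m lesions has inverse covariance (1/20)[I − 5/(20 + 5m) J], where J is the all-ones matrix. Contributions to the information matrix for the three means:

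| Patients | Diagonal | Off-diagonal |
|---|---|---|
| 12 with 3 lesions | 12 × (1/20) × (6/7) = 0.5143 | −12 × (1/20) × (1/7) = −0.0857 |
| 6 with 2 lesions | 4 × (1/20) × (5/6) = 0.1667 | −2 × (1/20) × (1/6) = −0.0167 |
| 12 with 1 lesion | 4/25 = 0.1600 | 0 |
| Total | 0.8410 | −0.1024 |

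For the weights (½, ½, −1), the variance is 1.5/(0.8410 + 0.1024) = 1.590, so the SE is 1.261.

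**Step 4: power for a difference of 3 days.**

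| Method | Test | Independent | Within-patient balance | Gain (points) |
|---|---|---|---|---|
| Known-variance GLS | one-sided | 71.5% | 76.9% | 5.3 |
| REML, 20,000 runs, z | one-sided | 71.6% | 77.7% | 6.1 |
| Known-variance GLS | two-sided | 60.1% | 66.2% | 6.1 |
| REML, 20,000 runs, z | two-sided | 61.0% | 67.5% | 6.5 |

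A 20/20/20 split without within-patient balance has one-sided power of 72.7% (GLS) or 73.0% (REML). So about 1 point of the gain is arm balance, and 4.1 to 4.7 points are due to balance within patient.

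**Step 5: sensitivity (GLS, one-sided).** The SAP gives no source for the ICC of 0.2. The gain is about 2.5 points at ICC 0.05, 3.5 at 0.1, 5.3 at 0.2, 6.9 at 0.3 and about 8 at 0.5. With an assumed mix of 36/6/4 patients (36 + 12 + 12 = 60 lesions) and ICC 0.2, it is about 3 points, of which about 2 go beyond arm balance.

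**The case against.** The strongest reply is that independence is never stated. The SAP sentence is a simulation setting, an equal chance is a marginal probability that a blocked list would also satisfy, and the SAP's SE of 1.331 lies nearer the 20/20/20 value (1.334) than the independent one (1.357). This stands in part. With 100 simulations the SE cannot settle the matter, but the documents support only the statement that the procedure is not described. A reader who infers that the protocol prescribes independent allocation, or leaves arm sizes to chance, goes beyond the text.

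Two other strong readings also fail. One is that the within-patient comparison is largely wasted because only 22% of three-lesion patients would get all three regimens. The primary contrast needs only placebo and some active regimen in the same patient, which 67% of three-lesion patients would have. Two-lesion patients cannot receive three regimens under any scheme. The planned mixed model uses both within- and between-patient information, and the SE differs by about 7%. The other is that balancing would rescue the stated power. At the SAP's settings it does not.

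The cost of balancing is guessability. Selection of patients or lesions is not the issue, because all sites are marked before syringes are prepared. Reporting is: a patient who recognises one lesion's regimen could infer something about the others, and every outcome is the patient's own rating. This remains as a modest cost to weigh against a few points of power.

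**Conclusion.** The point holds as a matter of efficiency and of incomplete description. Allocating lesions independently and analysing them with a mixed model is valid, and nothing in the documents suggests bias from it. Balance within patient would gain about 5 to 6.5 points of primary power at no cost in patients or lesions, and no ICC examined from 0.05 to 0.5 showed a loss.

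The size rests on independent allocation as the comparator, the SAP's 12/6/12 mix, SD 5 and ICC 0.2, and on the SAP model's assumption that treating one lesion does not affect another. The protocol allows 20 to 60 patients. If every patient had one lesion, the within-patient gain would be nil. Power after the change is 77-78% one-sided at the SAP's settings; the gap to 80% comes from the SAP's power report and needs its own correction.

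**What to change.** State the randomisation procedure in the protocol, whichever is used. If it can still be chosen, the recommended scheme is:
- three-lesion patients: the three regimens in random order across the lettered sites;
- two-lesion patients: two different regimens, drawn from a balanced list of the three pairs and placed in random order;
- one-lesion patients: permuted blocks.

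Keep the planned mixed model with a patient random effect. Restate power under the chosen scheme with many more than 100 simulated data sets and a range of ICC values.

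The cost is a new randomisation list and a short protocol passage. If enrolment has begun, the list can apply to the remaining patients. To limit inference from one lesion to another, do not disclose the within-patient restriction to the injector, and do not emphasise it to patients beyond what consent requires.

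### The SAP's 80% power for combined triamcinolone versus placebo is about 72–73% on its own settings; the 28% for the dose comparison is about 37%, and the sidedness of the final tests is not stated

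*SAP*

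**What the plan says.** The SAP's section on simulation settings generates 60 lesions in 30 patients from a random-intercept model. Both contrasts are tested one-sided at 5%: "report the probability of rejecting the null (one side p-value < 0.05". The replicate count is low: "After simulating the data 100 times, we fit the same model". For days to resolution the results table prints:

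- combined triamcinolone versus control: true value −3, SE 1.331, power 0.8;
- one concentration versus the other: true value −2, SE 1.540, power 0.28.

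The text draws the conclusion that "there is 80% power to test that the combined treatment groups have less number of the days than the control group". It then gives an average 95% interval for the combined contrast: "the control group is (2.6, 5.6) for days to resolution and (2.46, 3.52) for pain scores".

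The SAP's opening text repeats both power figures without any statement of simulation error: "demonstrating 80% power to demonstrate our primary aim" and, for the dose comparison, "The power to tell a difference between our 2 treatment groups is only 28" per cent. On the final analysis it says that "p-values for comparisons between each group will be calculated in the final analysis for each study end point". Neither that sentence nor the closing section, Final analysis of data, says whether those tests are one- or two-sided.

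**The concern.** A true difference, its standard error and the test level fix the power to a close approximation. In this table the three do not agree with the power printed beside them, in either row for days to resolution. The 80% is the only power justification given for the primary comparison. If it is really about 72–73%, a true 3-day benefit would be missed about 27–28% of the time rather than 20%, which matters when a null result is interpreted.

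The printed interval adds to the problem. A lower limit of 2.6 days suggests an effect bounded well away from zero, which an SE of 1.331 around a difference of 3 cannot give. And because sidedness is settled for the power calculation but not for the final tests, a reader cannot tell which power applies to the analysis that will be reported.

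**Working it through.** **Inputs** (all from SAP, Simulation settings for power analysis)

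- Lesions: 12×1 + 6×2 + 12×3 = 60 in 30 patients, each lesion randomised with equal chance to three arms.
- Means 6, 8 and 10 days: combined contrast (6 + 8)/2 − 10 = −3; dose contrast 6 − 8 = −2.
- Patient SD 5√0.2 = 2.236 and error SD 5√0.8 = 4.472: total SD 5, intraclass correlation 0.2.
- One-sided 5% test (critical value 1.645); 100 replicates.

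**Step 1: the standard errors reproduce.** Scenario 1 was rerun with 10,000 replicates (REML random-intercept fit, Wald z test). Mean SEs were 1.330 and 1.537, against 1.331 and 1.540 printed. The SE column is therefore not a misprint.

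**Step 2: power from the printed SEs**, using Φ(|difference|/SE − critical value).

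- Combined: 3/1.331 = 2.254. One-sided Φ(2.254 − 1.645) = 0.729; two-sided Φ(2.254 − 1.960) = 0.616.
- Dose: 2/1.540 = 1.299. One-sided Φ(1.299 − 1.645) = 0.365; two-sided Φ(1.299 − 1.960) = 0.254.
- Power of 0.80 one-sided would need an SE of 3/(1.645 + 0.842) ≈ 1.207.

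**Step 3: power by rerun.**

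| Comparison | SAP | Printed SE, one-sided | Rerun, one-sided | Rerun, 20 lesions per arm, one-sided | Two-sided 5% (same three methods) |
|---|---|---|---|---|---|
| Combined vs control | 0.80 | 0.729 | 0.719 | 0.730 | 0.616, 0.611, 0.623 |
| Dose vs dose | 0.28 | 0.365 | 0.363 | 0.377 | 0.254, 0.262, 0.274 |

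**Step 4: other readings of the method.** For the combined contrast at one-sided 5%, a t reference applied to the printed SE gives 71–72%, maximum likelihood fitting 71.5–73.1%, and ignoring clustering 70.7%. Forcing different arms within a patient gives 76.5%, but with an SE of 1.27 rather than the printed one. None is within 2 points of 80%. One-sided 10% overshoots, at 83.5%. Two-sided testing brings the dose comparison near 0.28 but puts the combined comparison near 0.61, so no single level explains both figures.

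**Step 5: simulation error.** Exact 95% intervals are 0.708–0.873 for 80/100 and 0.195–0.379 for 28/100. Both contain the recomputed values. With true power 0.73, 80 or more rejections in 100 occur about 7% of the time; with 0.365, 28 or fewer occur about 5% of the time. The two errors go in opposite directions, as chance would allow and a common mistake in scale would not.

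**Step 6: the interval.**

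- Days: 3 ± 1.96 × 1.331 = (0.39, 5.61); the rerun average is (0.39, 5.60). Printed: (2.6, 5.6), with midpoint (2.6 + 5.6)/2 = 4.1 rather than 3.
- Pain: 3 ± 1.96 × 0.266 = (2.48, 3.52). Printed: (2.46, 3.52), which fits.

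Only the lower limit for days is out of line.

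**The case against.** **The SAP disclosed its method.** It says it used 100 replicates, and the recomputed powers lie inside the simulation error of the printed ones. That is right, and the accurate description is too few replicates and a favourable draw, not a wrong formula. It explains the 80% but does not support it: the opening text states the figure without qualification, and no simulation error is given anywhere.

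**The printed SE may itself be noisy.** If that column is the standard deviation of 100 estimates rather than an average model-based SE, its 95% range is about 1.17–1.55 and the implied power runs from 0.62 to 0.82. This is a fair limit on the closed form taken alone. The rerun does not depend on the printed SE, however, and gives the same answer.

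**The limit 2.6 may be a slip for 0.26.** The interval (0.26, 5.6) has half-width 2.67 = 2.006 × 1.331 and centre 2.93, close to a t-based interval from 100 replicates. This is plausible, so the stored output should be checked. A lower limit of 2.6 is wrong either way.

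**Sidedness.** The hypotheses in the protocol's Study Aims are directional and the power tests are one-sided, so the two-sided figures are conditional only. That stands, and they are used here only to show what hangs on the missing statement.

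**Little changes in practice.** The dose comparison is weak at 28% or 37%, and the SAP accepts that. The shortfall in the primary power equals a true difference of about 3.3 days instead of 3, or a total SD of about 4.5 instead of 5, and neither input is sourced. All true, and the reason why only the stated figures need correcting.

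**Conclusion.** The concern holds. On the SAP's own assumptions and its own one-sided 5% test, power is about 72–73% for combined triamcinolone versus placebo, not 80%, and about 37% for the dose comparison, not 28%. The first error flatters the design and the second understates it. The lower limit of the average interval for days should be near 0.4, not 2.6. If the final tests turn out to be two-sided at 5%, the corresponding powers are about 61–62% and 25–27%, so a true 3-day difference would be missed about 38–39% of the time.

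These figures assume the SAP's means, variance components and mix of lesions per patient, lesions randomised independently or in equal arms, and a random-intercept model with a Wald test. That 100 replicates caused the discrepancy is an inference: it fits the numbers but cannot be proved from the text.

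**What to change.** 1. Rerun Scenario 1 with at least 5,000 replicates. The 95% simulation error is then about 1.96 × √(0.72 × 0.28/5,000) = ±1.2 points. Report the replicate count and that error.
2. State the sidedness and level of the final tests, in the opening text and in Final analysis of data.
3. Replace 80% and 28% in the opening text, the simulation section and the results table with the rerun figures for that level: expect about 72–73% and 37% if one-sided 5%, or about 61–62% and 25–27% if two-sided 5%.
4. Check the days-to-resolution interval against the simulation output and restate its lower limit from the rerun (about 0.4).

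The cost is a few minutes of computing and a few lines of SAP text. The stated primary power becomes less favourable. Enrolment, design and model stay as they are.
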